Coronary revascularization procedure and death information for cardiovascular events of interests must be collected in the eCRF that occur after signing the ICF through the EOS/Safety Follow-Up visit for this study, or 30 days (+ 3 days) after the last administration of evolocumab, whichever is later. Sites will be prompted for this information when necessary.

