- review of targeted concomitant therapy
- review of adverse events, serious adverse events, device-related adverse effects, and disease-related events. Any events that occurred between FOURIER EOS and day 1, if applicable, will be recorded on the Event eCRF.
- physical examination
- vital signs (sitting blood pressure and heart rate)
- body weight
- **coronary revascularization procedure and death information (sites will be prompted for this information when necessary)**
- CANTAB SWM, PAL, and RTI tests (subjects who participated in the EBBINGHAUS study only)
- blood draws for fasting lipids (\geq 9-hour fasting sample), ApoA1, ApoB, Lp(a), and FSH (only if required to ensure menopause [see [Exclusion Criterion 207](#)])
- blood draw or urine sample for a serum or urine pregnancy test (women of childbearing potential only)
- administration of evolocumab at study site (see [Section 6.2.1](#) for instruction and supervision of subjects), if applicable
- dispensing evolocumab (prefilled AI/Pens or PIs), if applicable

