9.2 Safety Event Reporting Procedures

9.2.1 Reporting Procedures for Disease-related Events

The investigator is responsible for ensuring that all disease-related events observed by the investigator or reported by the subject that occur after the FOURIER EOS visit through the EOS visit for this study (FOURIER OLE) or 30 days (+ 3 days) after the last administration of evolocumab, whichever is later, are **recorded** using the Event eCRF. Additionally, the investigator is required to report a fatal disease-related event on the Event eCRF.

All serious disease-related events will be recorded and reported to the sponsor or designee within 24 hours. The investigator will submit any updated serious disease-related event data to the sponsor within 24 hours of it being available.

Events assessed by the investigator to be related to the investigational product (evolocumab)/protocol-required therapies, and determined to be serious, require reporting of the event on the Event eCRF.

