 - time to ischemic fatal or non-fatal stroke or transient ischemic attack, whichever occurs first
 - time to the first fatal and non-fatal myocardial infarction
 - time to the first fatal and non-fatal stroke
- Non-mortality
 - time to the first coronary revascularization
- Mortality
 - time to cardiovascular death
 - time to coronary death
 - time to death by any cause

Censoring date

Endpoints are censored differently according to the endpoint **categories**. The censoring schema are described in below:

- censoring date for the composite and non-mortality endpoints is the EOS date in the OLE study.
- censoring (or time-to-event) for mortality endpoints are detained in appendix C.

Time-to-first-event Definition

For the time-to-first-event analysis based on combined the parent and OLE data, the events adjudicated as positive in the parent study and occurred prior to or on subject last confirmed survival status date in the parent study (i.e., primary analysis in the parent study; please see the definition in the parent study SAP version 3.1 dated Aug 09, 2016) are included in addition to the events reviewed as positive in the OLE study (defined as below).

For the time-to-first-event analysis based on the OLE data only, mortality events reviewed as positive and occurred prior to or on later of (the EOS date or last known survival status date from eCRF page(s) in this OLE study) and non-mortality events reviewed as positive and occurred prior to or on the EOS date are included.

- For those subjects who already experience such event in the parent study, their time to event and censor flag are same as those in the parent study.
- For those subjects who didn't experience such event in the parent study, the derivation of the time-to-event and censoring date is presented below

For analyses combined both the parent study and this OLE study		
Endpoint	Time-to-first-event for subjects with events	Censoring date for subjects without events
Composite or Non-mortality	First event onset date reviewed by CEC in OLE study – randomization date in the parent study +1	EOS date in OLE study
Mortality	Death endpoint date reviewed by CEC in OLE	For subjects who died not due to death endpoint, the censoring date is the death

	study – randomization date in the parent study +1	date (reviewed by CEC) in OLE study For remaining subjects, the censoring date is max (EOS date, last known survival status date from eCRF page(s)) in the OLE study

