For analyses based on OLE data only		
Composite or Non-mortality	First event onset date reviewed by CEC in OLE study – enrolment date in OLE study +1	EOS date in OLE study
Mortality	Death endpoint date reviewed by CEC in OLE study – enrolment date in OLE study +1	For subjects who died not due to death endpoint, the censoring date is the death date (reviewed by CEC) in OLE study For remaining subjects, the censoring date is max (EOS date, last known survival status date from eCRF page(s)) in the OLE study

Patient-years of follow-up for treatment emergent adverse events

For analyses based on combined both the parent study and this OLE study:

- 1) Subjects had events: date (first event) – date (first dose date in FOURIER) + 1
- 2) Subjects didn't have events: min [date (EOS in OLE), date (last dose date in OLE)+30] – date (first dose date in FOURIER) + 1

For analyses based on OLE study:

- 1) Subjects had events: date (first event in OLE) – date (first dose date in OLE) + 1
- 2) Subjects didn't have events: min [date (EOS in OLE), date (last dose date in OLE)+30] – date (first dose date in OLE) + 1

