8.3.2 Handling of Incomplete Dates

Missing and partially missing dates will be queried. **Partial/missing EOS dates will be imputed as the maximum of (last dose date of IP, vital signs assessments, lab assessments, AE start dates, concomitant medication start dates and imputed EOS date if partially missing).** Partial/missing onset dates (reviewed by CEC) of time-to-first-event endpoints will be imputed using the following algorithm, with the reference date being the enrollment date.

- Impose the missing year as the year of the reference date
- Impose the missing month as January
- Impose the missing day as 1st

Partial/missing start dates of adverse events and disease-related adverse events will be imputed using the following algorithm, with the reference date being the first dose date.

- Impose the missing year as the year of the reference date
- Impose the missing month as January
- Impose the missing day as 1st

If any of the resulting dates above are prior to the reference date, the imputed date will be reset to the reference date. **Please note for completely missing start dates of adverse-events and disease-related adverse where 'Did event start before first dose of investigational product?' on eCRF is recorded as 'Yes' will not be imputed. In addition, any imputed death dates will be the maximum of (the all adverse event start dates [use imputed event dates if missing], subject EOS dates**

[use imputed EOS dates if missing], and subject last confirmed survival status date recorded on the survival status eCRF page). For CEC death events and AE death event start dates, missing or partial missing dates will use the imputed death dates.

Adverse events with a valid answer to the question 'Did event start before first dose of investigational product?' on eCRF can be well defined based on the answer regardless of dates being completely or partially missing. Adverse events that cannot be determined as prior to IP or not either by the question above or by the onset date will be counted as treatment-emergent adverse events.

Concomitant medication with completely or partially missing start dates will be queried. After the query is resolved and the date is still incomplete with year only or year and month only, the start date will be imputed as described in [Table 8-1](#) below.

Table 8-1. Imputation Rules for Incomplete Dates

	Missing	Imputation	Exception

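### The OLE-only analysis of CEC-reviewed non-mortality and composite endpoints has no lower date limit, so an event before OLE enrolment can enter with a time of zero or less, or as a day-1 event

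*SAP*

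**What the plan says.** **Inclusion.** For the OLE-only analysis, SAP 5.1 (Time-to-first-event Definition) says that "non-mortality events reviewed as positive and occurred prior to or on the EOS date are included". Deaths have the same one-sided form: "mortality events reviewed as positive and occurred prior to or on later of" the EOS date and the last known survival status date.

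**Clock.** The table in SAP 5.1 gives the OLE-only time for composite and non-mortality endpoints as "First event onset date reviewed by CEC in OLE study – enrolment date in OLE study +1".

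**Incomplete dates.** SAP 8.3.2 imputes CEC onset dates "with the reference date being the enrollment date": a missing year becomes the enrolment year, a missing month January, a missing day the 1st. Then: "If any of the resulting dates above are prior to the reference date, the imputed date will be reset to the reference date".

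**Collection.** Protocol 9.2.1 and 9.2.2 start event collection after the FOURIER EOS visit. Protocol 7.2.1 adds: "Any events that occurred between FOURIER EOS and day 1, if applicable, will be recorded on the Event eCRF". For coronary revascularization and death information, Protocol 7.2 uses another start, covering events "that occur after signing the ICF through the EOS/Safety Follow-Up visit for this study". Protocol 3.1 and 10.4.1 send all cardiovascular events of interest to the CEC.

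**The gap elsewhere in the SAP.** SAP 9.7 plans a listing of events between parent-study EOS and OLE enrolment. It says that they are on the medical history eCRF.

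**Outputs.** SAP 9.5.3 asks for subject incidence, exposure-adjusted rates and yearly Kaplan-Meier estimates of CEC-positive events in the OLE-only period. That period is not defined.

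**The concern.** The inclusion rule and the clock do not match. The clock starts at enrolment, but the rule admits any CEC-positive event up to EOS, and event collection starts earlier, at FOURIER EOS. An MI in between satisfies the rule as written and has no valid time on the clock. Because the analysis takes the first event, that MI also removes the subject's later OLE event of the same endpoint.

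Treatment-emergent adverse events do not have this problem: SAP 5.3 bounds them below at first dose, and SAP 8.3.2 leaves a completely missing start date unimputed when the eCRF flags it as pre-dose. CEC events have neither safeguard. Two programmers could both follow the SAP and produce different OLE-only incidence, rates and Kaplan-Meier curves.

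**Working it through.** The plan gives no figure to reproduce here, so the check applies its rules to example records.

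**1. Complete onset date.** Time = onset − enrolment + 1 (SAP 5.1).

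| Onset relative to OLE enrolment | Time |
|---|---|
| same day | 1 |
| 1 day before | 0 |
| 7 days before | −6 |
| 30 days before | −29 |
| 90 days before | −89 |

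The reset in SAP 8.3.2 covers imputed dates only, so these values stand. The SAP does not say how to treat them. Software may drop the record, reject it or place it at the origin. The event still counts in crude incidence. If person-time to first event is taken from this formula, it adds zero or negative follow-up to the rate.

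**2. Partial onset date.** Take enrolment on 15 December 2016 as an example.

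- Onset recorded as November 2016: imputed to 1 November, reset to 15 December, time = 1. The record itself shows that onset preceded enrolment by 15 days (30 November) to 44 days (1 November).
- Onset recorded as December 2016, as 2016 only, or fully missing: also reset to 15 December, time = 1. Here the known part is compatible with onset on or after enrolment, so the reset is defensible.

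The reset is not limited to OLE-only analyses. In the combined analysis (onset − randomization + 1), the November event would sit 44 days later than its imputed date of 1 November.

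**3. Which interval matters.** Only onset between FOURIER EOS and OLE enrolment gives a time of zero or less. Protocol 7.2 allows up to 90 days from FOURIER EOS to day 1, which is first dose. Enrolment is the investigator's eligibility decision (Protocol 5) and may come earlier. Ninety days is therefore a ceiling borrowed from a longer interval.

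**4. Possible size.** The planned 5000 subjects are in the documents. The share with a gap, its length and the event rate are assumptions.

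Gap events = 5000 × share × (gap days / 365.25) × rate. First-year events ≈ 5000 × rate.

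- Low: 5000 × 0.10 × 30/365.25 × 0.03 = 1.2 events, against 5000 × 0.03 = 150, or 0.8%.
- High: 5000 × 0.50 × 90/365.25 × 0.06 = 37.0 events, against 5000 × 0.06 = 300, or 12.3%.

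The rate cancels in the percentage, which is share × gap/365.25, so the percentages reflect only the assumed gaps. If all gap events were placed at the origin, the curve would start with a step of 1.2/5000 = 0.02 to 37.0/5000 = 0.74 percentage points.

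**The case against.** **The SAP treats gap events as history.** SAP 9.7 puts them on the medical history eCRF and in a listing that Amendment 1 added on purpose. If so, they might never reach the CEC, whose charter is not available here and may set its own review window. This shows that eligibility is not certain. But a listing is not an exclusion, and Protocol 7.2.1 puts the same events on the Event eCRF. That section's medical-history rule covers adverse events ongoing from the end of FOURIER, not new ones. What remains is a conflict between the documents that the analysis rule does not settle.

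**The intended start is obvious.** The enrolment origin and the repeated references to OLE-only data do signal it. The clock origin is indeed defined; what is missing is a lower limit for inclusion. Intent does not settle partial dates either, because the stated reset moves a known pre-enrolment event to enrolment day.

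**A limit at enrolment still admits events between enrolment and first dose.** True. Those events have valid positive times on the SAP's own clock. Whether they should count as on-treatment is a separate question.

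**The endpoints are exploratory and descriptive.** This stands, and it limits the weight of the point. The primary endpoint already has its lower limit.

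**Conclusion.** The defect holds for OLE-only composite and non-mortality CEC endpoints. As written, a CEC-positive event with a complete date before enrolment is included with a time of zero or less and displaces a later OLE event. One with a partial date known to precede enrolment becomes a day-1 event. Pure mortality endpoints share the one-sided wording but are effectively unaffected, since a subject who died before enrolment could not be enrolled.

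The size is unknown and probably small: the protocol recommends day 1 on the day of the FOURIER EOS visit, and part of any gap may fall after enrolment. The range of about 1 to 37 events also assumes that gap events reach the CEC.

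A reader might infer three stronger things that the documents do not support:

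- That a material share of first-year events is wrong. The upper figure of 12.3% needs half of all subjects to have a full 90 days before enrolment, and nothing in the documents indicates that.
- That the error is confined to year 1. Kaplan-Meier estimates are cumulative, so an error at the origin carries forward, and the displaced event may belong to any year.
- That the combined FOURIER and OLE analysis is untouched. This is so for complete dates, but the reset slightly shifts partial ones.

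**What to change.** - **SAP 5.1, OLE-only analysis:** include only CEC-positive events with onset on or after the OLE enrolment date. State that a subject with an earlier gap event stays at risk for a later OLE event.
- **SAP 8.3.2:** apply the reset to a CEC onset date only when its known part is compatible with onset on or after enrolment. Otherwise exclude the event from the OLE-only analysis and keep it at its imputed pre-enrolment date in the combined analysis.
- **Protocol 7.2.1 and SAP 9.7:** reconcile which eCRF holds events between FOURIER EOS and enrolment, and state whether the CEC reviews them.

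The smallest possible OLE-only time is then 1 day. The analysis change costs two short additions to the SAP and one programming filter, with no new data. The reconciliation needs a check of how the records were entered and a clarifying sentence.

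### SAP 5.1 conflicts with itself on the OLE-only time-to-first-event analysis: two bullets that name no analysis bring in FOURIER event times, or leave those subjects with no OLE-only derivation

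*SAP*

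**What the plan says.** The time-to-first-event definition in SAP 5.1 has three parts.

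- **Inclusion paragraphs, one per analysis.** The combined paragraph takes in "the events adjudicated as positive in the parent study" as well as OLE events. The OLE-only paragraph adds no parent-study events; for nonfatal endpoints it says that "non-mortality events reviewed as positive and occurred prior to or on the EOS date are included".
- **Two bullets, directly after the OLE-only paragraph, with no analysis named.** The first covers subjects "who already experience such event in the parent study, their time to event and censor flag are same as those in the parent study". The second reads: "For those subjects who didn't experience such event in the parent study, the derivation of the time-to-event and censoring date is presented below".
- **A derivation table with two blocks.** The combined block counts time from FOURIER randomization. The block headed "For analyses based on OLE data only" subtracts "enrolment date in OLE study +1" from the onset of the first CEC-reviewed OLE event.

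SAP 9.5.3 plans yearly Kaplan-Meier (K-M) estimates of CEC-positive events for the OLE-only period and for the combined period. SAP 9.1 places all analyses on the OLE safety analysis set. Protocol 10.4.1 makes OLE data the basis of the primary analysis of every endpoint, exploratory ones included.

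**The concern.** The inclusion paragraphs and the OLE-only row describe one analysis; the bullets describe another. Read literally, the first bullet also governs the OLE-only analysis. The second keeps any subject with a FOURIER event out of the table, including its OLE-only block.

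If that were programmed, an estimate labelled as OLE data would contain FOURIER events, some of them from subjects then on placebo. It would place times counted from FOURIER randomization on the same axis as times counted from OLE enrolment, and it would discard later OLE events in the same subjects. The SAP's change log says these definitions were added so that OLE results could be compared with FOURIER results. An OLE-only curve that already holds FOURIER events cannot serve that purpose.

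**Working it through.** The plan gives no figure on this point to reproduce. The check is a side-by-side reading, a count of endpoints and a conditional size.

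**1. One subject, three readings.** Take a subject with a nonfatal FOURIER MI who enters the OLE, and consider the OLE-only MI endpoint.

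| Reading | Result |
|---|---|
| Inclusion paragraph and OLE-only row | Followed for a first OLE MI from OLE enrolment |
| Both bullets as written | Event at the FOURIER time; any OLE MI unused |
| First bullet taken as combined-only, second unchanged | No OLE-only derivation |

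With invented dates: a FOURIER MI on FOURIER day 200 and an OLE MI 399 days after OLE enrolment give 399 + 1 = day 400 under the row and day 200 under the bullets. With no OLE MI, the subject is censored at OLE end of study under the row and is still an event at day 200 under the bullets.

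**2. Endpoints exposed.** SAP 5.1 lists 6 composite + 1 non-mortality + 3 mortality = 10. Each composite has a nonfatal component, and coronary revascularization can be nonfatal. Protocol 4.1.1 requires completion of FOURIER on assigned product, and no criterion in 4.1.2 bars a nonfatal FOURIER event as such. So 6 + 1 = 7 can already have occurred. The 3 mortality endpoints cannot have occurred in someone who enrolled.

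**3. Size with complete 5-year follow-up (assumption).** Let q be the share of OLE subjects with a nonfatal FOURIER event timed within 5 years of randomization, and R their 5-year OLE risk. K-M then equals a simple proportion. The bullets count all of these subjects as events; the row counts a share R. The overstatement is q − qR = q(1 − R), which is at most q. The documents give neither q nor R.

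For q = 1% of 5000 = 50 subjects:
- R = 0: 1.0 point
- R = 0.10: 0.01 × 0.90 = 0.9 points; 50 × 0.10 = 5 OLE first events unused
- R = 0.30: 0.01 × 0.70 = 0.7 points; 50 × 0.30 = 15 unused

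A simulation of 5000 subjects agrees. It assumed an OLE hazard of 2% per year, FOURIER event times uniform over 0 to 2 years, and no censoring before year 5. The 5-year estimate moved from 9.6% to 11.4% at q = 2% and from 9.6% to 14.1% at q = 5%. With R = 1 − exp(−0.10) = 0.095, the formula gives 0.02 × 0.905 = 1.8 and 0.05 × 0.905 = 4.5 points, the same rises.

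**4. Size with censoring.** Take the same 50 subjects, with FOURIER events timed at year 2 and no OLE events, and 4950 others with no events. All of this is assumed.
- 10% of the others censored at year 1: 4455 remain, and the rise is 50/(4455 + 50) = 1.11 points
- 50% censored at year 1: 2475 remain, and the rise is 50/(2475 + 50) = 1.98 points

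The ceiling of 1.0 point per 1% therefore does not carry over to K-M with censoring.

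**The case against.** The strongest reply is that this is a missing label, not a rule anyone would follow. Only the combined analysis admits parent-study events. The OLE-only row names only OLE events and OLE enrolment. The combined paragraph points forward for its definition of OLE events, so the bullets can be read as resuming the combined derivation. The neighbouring person-time rule for adverse events does separate the two analyses, using "Subjects had events: date (first event in OLE" and the OLE first dose for the OLE one. Page layout might also tie the bullets to one analysis.

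Most of this stands as evidence of intent, but it does not repair the text. No words limit the bullets, and the second one leads into a table that holds both blocks. Reading only the first as combined-only leaves subjects with a FOURIER event without an OLE-only rule. Dropping them would conflict with SAP 9.1.

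Three stronger inferences are tempting and not supported:
- A reader might infer that seven OLE-only curves are wrong. Seven is the number of endpoint definitions exposed. SAP 9.5.3 does not say which will be shown as OLE-only K-M curves, and Table 9-1 lists no multi-component composite.
- A reader might take SAP 8.3.2 as proof of intent, because missing CEC onset dates for "time-to-first-event endpoints will be imputed using the following algorithm, with the reference date being the enrollment date". OLE events enter both analyses, so that rule fits either reading.
- A reader might infer that the OLE-only results were in fact produced this way. The documents do not show how the rule was programmed.

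**Conclusion.** The inconsistency is real, and the bullets are wrong as written for the OLE-only analysis, although they were very likely meant for the combined one. It should be fixed, at modest priority: the affected endpoints are exploratory and descriptive, and no test depends on them. The mortality endpoints, the combined analysis and the primary adverse-event endpoint are unaffected.

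Any distortion arises only if the bullets are applied literally, and its size cannot be fixed because the documents give no FOURIER event counts for OLE subjects. The conditional statement is q(1 − R) at 5 years under complete follow-up. Treating its ceiling of q as a general bound would be an error, as the 1.11 and 1.98 point examples show.

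**What to change.** Amend SAP 5.1 as follows.

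- Limit both bullets to the combined parent and OLE analysis.
- State that the OLE-only block applies to every subject in the OLE safety analysis set, whatever happened in FOURIER: the event is the first CEC-positive OLE event, timed from OLE enrolment, with censoring otherwise as in the table.
- State separately how an event between FOURIER end of study and OLE enrolment is handled, consistently with the separate listing in SAP 9.7. The present row would give such an event a time of zero or less (onset one day before enrolment: −1 + 1 = 0).

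The cost is one paragraph of SAP text and a check of the derivation program against it. No new data are needed.

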3.1 Study Design

This is a multicenter, open-label extension study designed to assess the long-term safety of evolocumab in subjects who completed the FOURIER study (Study 20110118), a randomized placebo-controlled study of evolocumab in subjects with clinically evident

atherosclerotic CVD on stable effective statin therapy. Eligible subjects at sites participating in FOURIER OLE who have signed the FOURIER OLE informed consent may be enrolled at the completion of FOURIER. Enrollment of eligible subjects may be limited at the site level to maintain a 1:1 ratio between the following subject populations:

- subjects with \geq 2 years of study exposure in FOURIER and
- subjects who have less than 2 years of study exposure in FOURIER and did not participate in EBBINGHAUS

In this study (FOURIER OLE), laboratory assessments will be performed at week 12 and thereafter approximately every 24 weeks from day 1; the corresponding blood samples will be processed using a central laboratory. To preserve the integrity of FOURIER blinding, no local lipid assessments may be performed until either FOURIER is unblinded or at least 12 weeks after a subject's last administration of FOURIER investigational product (evolocumab or placebo), whichever is first.

Upon enrollment in this study (FOURIER OLE), subjects will receive evolocumab 140 mg every 2 weeks (Q2W) or 420 mg monthly (QM), according to their preference. Frequency and corresponding dose of administration can be changed at any scheduled time point where evolocumab is supplied to the subject, provided the appropriate supply is available. It is recommended that subjects continue the same background LLT, including statin, as taken during FOURIER.

This study will continue for 260 weeks (approximately 5 years). Subjects ending administration of evolocumab should continue study assessments until the end of study (EOS).

All subjects will be followed and complete procedures/assessments from enrollment through the date of study termination unless the subject has withdrawn consent, irrespective of whether the subject is continuing to receive treatment. All deaths and cardiovascular events of interest (MI, stroke, coronary revascularization, hospitalization for unstable angina, hospitalization for heart failure, and transient ischemic attack [TIA]) will be reviewed by an independent external Clinical Events Committee (CEC), using standardized definitions.

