5.1 Study Time Points

Baseline

The baseline value is defined as the subject's baseline value from the parent study, unless otherwise specified.

First Dose Date of Investigational Product (IP)

For each subject, the first dose date of IP is the date of the first administration of evolocumab in this OLE study.

End of Investigational Product (EOIP) Date

For each subject, end of investigational product is the date reported on End of Investigational Product Administration eCRF.

Last Dose Date of Investigational Product

For each subject, the last dose date of investigational product is defined as the date of the last administration of investigational product (evolocumab or placebo).

If the last dose was administered in-clinic, then the Last IP Dose Date is the last start date captured on the IP Administration (In-Clinic) eCRF page.

If the last dose was administered at a non-investigator site location, then the Last IP Dose Date is defined as the final dose date reported by the subject on the Non-Clinic Final Investigational Product Dose Date eCRF page.

End of Study (EOS) Date

For individual subject, the end of study date is defined as the last day that protocol-specified procedures are conducted for an individual subject, including safety follow-up and survival assessment. The EOS date is recorded on the End of Study eCRF.

Enrollment Date

The enrollment date for each subject is recorded on the Subject Enrollment eCRF **in the OLE study.**

Study Day 1

The date of the first administration of evolocumab in the OLE study or the **enrollment date** for subjects who are not administered any dose of evolocumab.

Study Day

For each subject, and for a given date of interest, study day is defined as the number of days since study day 1:

Study day = (date of interest – study day 1 date) + 1

If the date of interest is prior to the study day 1:

Study day = (date of interest – study day 1 date)

Study End Date

The study end date is the last EOS date of all enrolled subjects.

Endpoint Categories

All time-to-**first**-event endpoints in this study are categorized below.

- Composite
 - time to cardiovascular death, myocardial infarction, hospitalization for unstable angina, stroke, or coronary revascularization, whichever occurs first
 - time to cardiovascular death, myocardial infarction, or stroke, whichever occurs first
 - time to cardiovascular death or hospitalization for worsening heart failure, whichever occurs first

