9.5.3 Analyses of Exploratory Endpoints

In subjects who completed the EBBINGHAUS study (Study 20130385), descriptive statistics for the exploratory endpoints (raw score and change from baseline of SWM strategy index of executive function, SWM between-errors score, PAL total errors adjusted and RTI median 5-choice reaction time) will be provided by each scheduled visit for OLE CANTAB analysis set.

The change and percent change from baseline in lipid parameters at each scheduled visit will be summarized based on the OLE Safety Analysis Set for the **combined parent and OLE study periods.** For continuous exploratory endpoints, summary statistics (number of subjects, mean, median, standard deviation or standard error, first and third quartiles, minimum, and maximum) at all scheduled visits will be calculated. Subject incidence, exposure-adjusted subject incidence rate, and yearly Kaplan Meier (K-M) estimates of positively reviewed events (by an independent external CEC) will be summarized **for both the OLE only study period and combined parent and OLE study periods.** All deaths will be summarized by cardiovascular death (including coronary heart disease death), non-cardiovascular death and undetermined cause of death.

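### Yearly Kaplan-Meier estimates for cardiovascular and coronary death censor other deaths and so modestly overstate cumulative incidence within the OLE cohort

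*SAP*

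**What the plan says.** SAP 9.5.3 states that, besides subject incidence and exposure-adjusted rates, "yearly Kaplan Meier (K-M) estimates of positively reviewed events (by an independent external CEC) will be summarized", for the OLE-only and the combined parent-plus-OLE periods.

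SAP 5.1 sets the censoring by endpoint category:

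- **Mortality** (CV death, coronary death, all-cause death). "For subjects who died not due to death endpoint, the censoring date is the death" date as reviewed by the CEC. The same rule is given for both periods.
- **Composite and non-mortality.** The "censoring date for the composite and non-mortality endpoints is the EOS date in the OLE study". Death is not mentioned. The EOS definition reads: "For individual subject, the end of study date is defined as the last day that protocol-specified procedures are conducted for an individual subject", which suggests, without saying so, that a subject who dies is censored at about the date of death.

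The only endpoint classed as non-mortality is "time to the first coronary revascularization". The composite category includes three endpoints that count CV death, and MI and stroke endpoints that count fatal events.

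Neither document names a cumulative incidence function or any other competing-risk method. The Appendix C figure on mortality censoring is not in the available text, so this point rests on the tables in SAP 5.1.

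**The concern.** A subject who has died of cancer cannot later die of coronary disease. K-M with such deaths censored redistributes that subject's future risk to those still alive. It is a valid estimate of net risk, meaning risk if other deaths were removed, but it is not the proportion of patients who have the event by a given year.

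This matters because the study is descriptive. The exploratory objective (Protocol 1.3) is to describe the subject incidence of death and cardiovascular events, and there is no test or hazard ratio for which cause-specific censoring would be the natural choice. A reader will take a year-5 figure for CV death as the share of patients who had died of CV causes by year 5. With deaths censored, that figure is too high, by an amount that grows with follow-up and with the competing death rate.

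**Working it through.** **Yardstick from the plan.** The only design figure is SAP Table 3-1, the 95% confidence interval width with N = 5000. At a 5% rate: 2 × 1.96 × √(0.05 × 0.95 / 5000) = 1.208%, as printed. It is not an input below; it only gives a sense of scale.

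**Inputs.** Follow-up in the OLE is 260 weeks, taken as T = 5 years (SAP 3.1). The documents give no event or death rates, so all hazards are assumptions, taken as constant.

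**Formulas.** With event hazard h and competing death hazard c:

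- one minus K-M = 1 − exp(−hT)
- cumulative incidence = h/(h + c) × [1 − exp(−(h + c)T)]

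**Worked cases, OLE only, T = 5.**

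- CV death, h = 1%/y: K-M = 1 − exp(−0.05) = 4.88%.
  - c = 1.5%/y: 0.4 × [1 − exp(−0.125)] = 4.70%. Excess 0.18 points, 3.8% relative.
  - c = 2%/y: 0.333 × [1 − exp(−0.15)] = 4.64%. Excess 0.23 points, 5.0% relative.
- Revascularization, h = 2%/y, all deaths c = 2.5%/y (if deaths are censored): K-M = 1 − exp(−0.10) = 9.52%; incidence = 0.444 × [1 − exp(−0.225)] = 8.95%. Excess 0.56 points, 6.3% relative.

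**Range at 5 years under other assumed rates.**

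| Endpoint | h per year | Competing death c per year | One minus K-M | Cumulative incidence | Relative excess |
|---|---|---|---|---|---|
| CV death | 1% | 0.5% to 3% | 4.88% | 4.82% to 4.53% | 1.2% to 7.6% |
| Coronary death | 0.5% | 1.5% to 4% | 2.47% | 2.38% to 2.24% | 3.8% to 10.3% |
| Revascularization | 2% | 2% to 5% | 9.52% | 9.06% to 8.44% | 5.0% to 12.8% |
| Five-part composite | 4% | 1% to 3% (non-CV death) | 18.13% | 17.70% to 16.88% | 2.4% to 7.4% |

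The relative excess is roughly cT/2. A simulation of 2 million subjects with h = 2%/y, c = 3%/y and T = 5 gave 9.516% and 8.848%, as the formulas do.

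**Combined period.** Inclusion criterion 102 requires completion of FOURIER, so no analysed subject died in it. Assume 2 years in FOURIER, then 5 in the OLE.

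- Revascularization, same hazards: K-M = 1 − exp(−0.14) = 13.06%. The incidence is [1 − exp(−0.04)] + exp(−0.04) × 8.95% = 3.92% + 8.60% = 12.52%. Gap 0.54 points.
- CV death, h = c = 1%/y: no deaths in the first 2 years, so K-M at year 7 is still 4.88%. The incidence given survival to the OLE is 4.76%. The incidence from randomization in an unselected cohort would be 0.5 × [1 − exp(−0.14)] = 6.53%.

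For combined-period mortality read as risk from randomization, the net bias is therefore downward, and it comes from selection rather than from the estimator.

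**The case against.** The defence has real weight.

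- **K-M is not the only output.** A reader might infer that the yearly estimate is all that this analysis yields. SAP 9.5.3 also plans subject incidence and exposure-adjusted rates, and subject incidence is the endpoint that the protocol defines. Neither treats the dead as still at risk. This stands, and it confines the point to the yearly, time-specific estimates.
- **Not every reported risk is too high.** K-M is correct for "time to death by any cause". Combined-period mortality read from randomization errs downward.
- **Seven-year gaps.** A reader might run both hazards for 7 years from randomization: for CV death with c = 1.5%/y, 6.76% against 6.42%; for revascularization, 13.06% against 12.01%. The documents do not support this, because no analysed subject died in FOURIER. With 2 of the 7 years there, the gaps are 0.18 points, not 0.34, and 0.54, not 1.05. Moreover, only about 2000 of the 5000 subjects were expected to have at least 2 years in FOURIER (Protocol 2.3).
- **Additivity.** A reader might infer that CV and non-CV death curves will sum to more than all-cause mortality. Non-CV death is not on the SAP 5.1 list of time-to-event endpoints, so a K-M curve for it is not clearly planned.
- **Size and continuity.** The excess for CV death is small beside the 1.208-point interval width, the endpoints are exploratory, and the SAP change log says that the time-to-event definitions were added so that OLE and FOURIER results could be compared. All true. But the excess is systematic, does not shrink with sample size, and can be removed without giving up the comparison.

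**Conclusion.** The point holds in a limited form. For CV and coronary death the censoring rule is explicit, and yearly one minus K-M will exceed cumulative incidence within the OLE cohort. For revascularization and the composites the same follows only if subjects who die are censored at about death through the EOS date, which is an inference. The relative effect on composites that count CV death is smaller, since only non-CV deaths compete; for the MI and stroke endpoints, deaths outside the component compete.

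Under the main assumed rates the excess at 5 years is 0.18-0.23 points for CV death (about 4-5% relative) and 0.56 points for revascularization. These sizes rest on constant hazards that the documents do not supply. The direction, for a fixed cohort and time origin, does not depend on them. This is a worthwhile refinement of an exploratory display and does not affect the primary endpoint.

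**What to change.** - **SAP 9.5.3:** report yearly Aalen-Johansen cumulative incidence for every endpoint except all-cause death, with death outside the endpoint as a competing event, for both periods.
- **SAP 5.1:** state how a death outside the endpoint is handled for composite and non-mortality endpoints, rather than leaving it to the EOS date.
- **Keep K-M** for all-cause death, and elsewhere as a secondary display for comparison with FOURIER, footnoted as a net risk.
- **Separately**, note beside the combined-period mortality figures that every analysed subject survived FOURIER by design. Aalen-Johansen does not correct this.

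The cost is SAP wording and a standard procedure; the events and CEC-reviewed deaths are already collected. The downside is that the main figures would differ in method from those of the parent study, which the secondary K-M display covers.
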